#### Study Visit - 4 weeks (+/-1 week) preoperative

The patients will undergo their allocation treatment during this time

- Oral Iron
  - Patients will take their oral iron supplementation as prescribed starting from 3-5 weeks preoperatively until the day before surgery
- Intravenous Iron
  - Patients will appointments at the Medical Day unit (MDU) at the Women's and Children's Hospital will be made 3-5 weeks preoperatively.
  - Upon arrival at MDU patients will have a baseline set of vitals collected, they will undergo intravenous cannulation by the orthopaedic resident medical officer, and then receive the intravenous ferric carboxymaltose as described previously.
  - Following the infusion patients will remain in MDU for 45minutes where their vitals will be regularly monitored.

#### Day of Surgery

Patients will present to the Women's and Children's hospital in the usual fashion

- They will then undergo routine measure of vital signs
- Following intravenous cannulation by the attending anaesthetist blood will be collected for:
  - Full Blood Exam
  - Iron Studies
  - Electrolytes including Calcium, Magnesium and Phosphate ("ELC")
- Surgical and Anaesthetic data will be collected including:
  - ASA status
  - Estimated Blood Loss
  - Cell Salvage Volume returned to patient
  - Duration of surgery
  - Number of spinal levels fused
  - Transfusion volume and product type

#### In hospital - Day 1 Postoperative

Patients will undergo routine:

- Measure of vital signs
- Collection of blood for Full Blood Exam
- Documentation of any transfusion

#### Prior to discharge - Day 5 (+/-2 days) Postoperative

Patients will undergo routine:

- Measure of vital signs
- Collection of blood for Full Blood Exam

- This will occur one day prior to discharge or at 7 days postoperatively (whichever is sooner)
- Documentation of any transfusion
- Patients will be asked to complete their oral iron therapy compliance questionnaire

#### Wound review visit 3 weeks (+/-1week) Postoperatively

Patients will present to Women's and Children's hospital for routine wound review by their surgeon. At this appointment we will collect:

- Collection of blood for Full Blood Exam

#### Final Study visit 12 weeks (+/- 4 weeks) Postoperatively

Patients will present to Women's and Children's hospital for routine follow up by their surgeon. At this appointment we will:

- Measure vitals
- Document height and weight
- Collection blood for Full Blood Exam, Iron Studies and Electrolytes including Calcium, Magnesium and Phosphate ("ELC")
- Collect follow up SRS 30 Questionnaire

## 8.2. SAFETY AND OTHER ASSESSMENTS

### Intravenous Carboxymaltose

Patients presenting for their infusion of IV ferric carboxymaltose will have a baseline set of vital signs recored by the MDU nurses. They will continue to have their vitals monitored during and for 45 minutes following the infusion.

Any vitals outside the acceptable range (according to the age appropriate RDR chart) will result in the infusion being stopped and the orthopaedic resident medical officer or medical emergency team being contacted for further advise. Any evidence or report of difficulties breathing or a developing rash will result in the immediate discontinuation of the infusion and the medical emergency team will be called to review the patient.

Patients and their parents will be provided with a contact number for one of the investigators and encouraged to report any adverse events/side effects.

All adverse events will be recorded on the patient data sheet and immediately feedback to the investigators.

### Oral Iron Therapy

When patients or their parents collect their oral iron tablets they will be given an information sheet containing potential side effects as well as advise on how to manage these. These forms will contain the contact details of one of the investigators and patients are encouraged to report any adverse events.

## 8.3. ADVERSE EVENTS AND SERIOUS ADVERSE EVENTS

### 8.3.1. DEFINITION OF ADVERSE EVENTS (AE)

Adverse event means any untoward medical occurrence associated with the use of an intervention in humans, whether or not considered intervention-related.

---

### 8.3.2. DEFINITION OF SERIOUS ADVERSE EVENTS (SAE)

An adverse event (AE) or suspected adverse reaction is considered "serious" if, in the view of either the investigator or treating clinician, it results in any of the following outcomes: death, a life-threatening adverse event, inpatient hospitalisation or prolongation of existing hospitalisation, or a persistent or significant incapacity or substantial disruption of the ability to conduct normal life functions. Important medical events that may not result in death, be life-threatening, or require hospitalisation may be considered serious when, based upon appropriate medical judgment, they may jeopardise the participant and may require medical or surgical intervention to prevent one of the outcomes listed in this definition. Examples of such medical events include allergic bronchospasm requiring intensive treatment in an emergency room or at home, blood dyscrasias or convulsions that do not result in inpatient hospitalisation, or the development of drug dependency or drug abuse.

---

### 8.3.3. CLASSIFICATION OF AN ADVERSE EVENT

---

#### 8.3.3.1. SEVERITY OF EVENT

For adverse events (AEs) not included in the protocol defined grading system, the following guidelines will be used to describe severity.

- **Mild** - Events require minimal or no treatment and do not interfere with the participant's daily activities.
- **Moderate** - Events result in a low level of inconvenience or concern with the therapeutic measures. Moderate events may cause some interference with functioning.
- **Severe** - Events interrupt a participant's usual daily activity and may require systemic drug therapy or other treatment. Severe events are usually potentially life-threatening or incapacitating. Of note, the term "severe" does not necessarily equate to "serious".

---

#### 8.3.3.2. RELATIONSHIP TO STUDY INTERVENTION

All adverse events (AEs) must have their relationship to study intervention assessed by the clinician who examines and evaluates the participant based on temporal relationship and his/her clinical judgment. The degree of certainty about causality will be graded using the categories below. In a clinical trial, the study product must always be suspect.

- **Related** - The AE is known to occur with the study intervention, there is a reasonable possibility that the study intervention caused the AE, or there is a temporal relationship between the study intervention and event. Reasonable possibility means that there is evidence to suggest a causal relationship between the study intervention and the AE.
- **Not Related** - There is not a reasonable possibility that the administration of the study intervention caused the event, there is no temporal relationship between the study intervention and event onset, or an alternate aetiology has been established.

---

#### 8.3.3.3. EXPECTEDNESS

The principle investigators will be responsible for determining whether an adverse event (AE) is expected or unexpected. An AE will be considered unexpected if the nature, severity, or

frequency of the event is not consistent with the risk information previously described for the study intervention.

---

#### 8.3.4. TIME PERIOD AND FREQUENCY FOR EVENT ASSESSMENT AND FOLLOW-UP

The occurrence of an adverse event (AE) or serious adverse event (SAE) may come to the attention of study personnel during study visits and interviews of a study participant presenting for medical care, or upon review by a study monitor.

All AEs including local and systemic reactions not meeting the criteria for SAEs will be captured on the appropriate data collection form. Information to be collected includes event description, time of onset, clinician's assessment of severity, relationship to study product (assessed only by those with the training and authority to make a diagnosis), and time of resolution/stabilisation of the event. All AEs occurring while on study must be documented appropriately regardless of relationship. All AEs will be followed to adequate resolution.

Any medical condition that is present at the time that the participant is screened will be considered as baseline and not reported as an AE. However, if the study participant's condition deteriorates at any time during the study, it will be recorded as an AE.

Changes in the severity of an AE will be documented to allow an assessment of the duration of the event at each level of severity to be performed. AEs characterised as intermittent require documentation of onset and duration of each episode.

Investigators will record all reportable events with start dates occurring any time after informed consent is obtained until 7 (for non-serious AEs) or 30 days (for SAEs) after the last day of iron therapy. At each study visit, the investigator will inquire about the occurrence of AE/SAEs since the last visit. Events will be followed for outcome information until resolution or stabilisation.

---

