Description of Sites/ Facilities Enrolling Participants:	This study will be conducted at the Women's and Children's Hospital in Adelaide, Australia. This is a 314 bed tertiary level paediatric hospital.	

Description of Study Intervention:	
Patients who are found to be iron deficient on preoperative screening will be randomised to receive either oral iron therapy (control) or intravenous (IV) ferric carboxymaltose iron (intervention).
 
The dose of oral iron therapy will be 3-6mg/kg/day of elemental iron in the form of Ferrous Sulphate liquid or Ferrous Fumarate tablets administered for at least 3-5 weeks preoperatively. The dose of IV ferric carboxymaltose will be determined based on patient weight and haemoglobin (see below) this will be administered 3-5 weeks preoperatively.

Study Duration:	Estimated 36 months.
Participant Duration:	5 months

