1.2. SCHEMA

**1.3. SCHEDULE OF ACTIVITIES (SOA)**

Procedures	Enrolment/ Visit 1, Day -42 (+/- 14 days)	Group identification, Day -35 (+/- 14 days)	Study Visit 2, Day -28 (+/- 7 days)	Day Before Surgery Day -1	Day of Surgery Day 0	In hospital Days 1-5	Discharge Day 5 (+/- 2days)	Study Visit 3 Day 21 (+/- 7 days)	Final Study Visit 4 Day 63 (+/- 14 days )
Informed consent	X								
Demographics	X								
Medical history	X								
Baseline screening bloods	X								
Interpretation of bloods		X							
Randomization		X							
Administer study intervention - Intravenous iron therapy (IV arm only)			X						
Administer study intervention - Oral iron therapy (Oral arm only)		X-----X							
Vital signs	X		X		X	X	X		X
Height	X								X
Weight	X								X
SRS 30 Questionnaire	X								X
Full Blood Exam	X				X	X	X	X	X
Iron Studies	X				X				X
Electrolytes (“ELC”)	X				X				X
Vitamin D Level	X								
Surgical data - ASA, spinal levels, blood loss, cell salvage volume					X				
Transfusion volume					X	X	X		
Oral Iron Compliance Questionnaire						X			
Adverse event review and evaluation	X	X-----X							X
Data Entry	X	X	X		X	X	X	X	X

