#### 8.3.5. ADVERSE EVENT REPORTING

All adverse events will be recorded and collated by the investigators. The data will be collected from each participants data sheet that is completed at each of their study visits. The incidence of expected adverse events will be reported in the published data along with the occurrence and incidence of unexpected adverse events.

---

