**How many days per week did your child experience the following symptoms?**

Side Effects	Everyday (7days)	Most Days (5-7days)	Some Days (3-4days)	Rarely (1-2days)	None (0days)
Nausea					
Constipation					
Diarrhea					
Abdominal Pain					
Other					

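### Section 8.3.4 contradicts itself on when adverse-event recording ends, and its explicit cut-off closes non-serious recording before surgery in the IV arm but after surgery in the oral arm

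*Protocol*

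**What the plan says.** Section 8.3.4 opens recording at the same point in both arms, for events "with start dates occurring any time after informed consent is obtained", and closes it "until 7 (for non-serious AEs) or 30 days (for SAEs) after the last day of iron therapy".

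The last day of iron differs by arm. The Synopsis says of the IV dose that "this will be administered 3-5 weeks preoperatively", and the Schedule of Activities puts it at Day -28 +/- 7. Section 6.1.2 provides for two doses a week apart when the calculated amount exceeds the single-dose limit. For the oral arm, section 8.1 says "Patients will take their oral iron supplementation as prescribed starting from 3-5 weeks preoperatively until the day before surgery".

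Two other statements set a wider scope. Section 8.3.4 itself says "All AEs occurring while on study must be documented appropriately regardless of relationship" and has the investigator ask about events at every study visit. The Schedule row "Adverse event review and evaluation" is marked at enrolment and at the final visit, with a span between, and does not distinguish the arms.

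On use of the data, section 8.3.5 says "The incidence of expected adverse events will be reported in the published data". Section 10.1.6 has events presented to the ethics committee at least twice a year to assess each arm.

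**The concern.** A site cannot follow both rules. A non-serious event that starts on Day 30 is recordable in either arm under the broad statement and in neither arm under the cut-off.

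If staff follow the cut-off, the arms are observed over different calendar periods, and the difference falls around surgery, when events of any cause are most likely to cluster. Section 8.3.3.2 allows a temporal relationship alone to make an event related, and section 2.3.1 lists nausea, vomiting and constipation as effects of oral iron. The same postoperative nausea on Day 2 would be recordable, and open to attribution to iron, in the oral arm; in the IV arm it would not be recorded. An IV-oral comparison of event incidence would then partly reflect the recording rule.

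The protocol says that the case for IV iron depends on whether its additional risk can be justified, so a rule that thins out IV events matters.

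**Working it through.** **Inputs.** Day 0 is surgery. Consent is nominally Day -42 (Schedule). The first iron day is Day -35, -28 or -21 in either arm (Schedule; section 8.1). The last iron day is the first day for a single infusion, the first day + 7 for a divided infusion (section 6.1.2), and Day -1 for oral (section 8.1).

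**Formulas.** Window end = last iron day + 7 (non-serious) or + 30 (serious). Length = window end minus start day.

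| Regimen | First iron day | Last iron day | Non-serious end | Days from first dose | Serious end | Days from first dose |
|---|---|---|---|---|---|---|
| IV single | -35 | -35 | -28 | 7 | -5 | 30 |
| IV single | -28 | -28 | -21 | 7 | +2 | 30 |
| IV single | -21 | -21 | -14 | 7 | +9 | 30 |
| IV divided | -35 | -28 | -21 | 14 | +2 | 37 |
| IV divided | -28 | -21 | -14 | 14 | +9 | 37 |
| IV divided | -21 | -14 | -7 | 14 | +16 | 37 |
| Oral | -35 | -1 | +6 | 41 | +29 | 64 |
| Oral | -28 | -1 | +6 | 34 | +29 | 57 |
| Oral | -21 | -1 | +6 | 27 | +29 | 50 |

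**From consent**, where section 8.3.4 starts the clock, with a single infusion on Day -28:
- Non-serious: IV -21 + 42 = 21 days; oral 6 + 42 = 48 days; ratio 48/21 = 2.3.
- Serious: IV 2 + 42 = 44 days; oral 29 + 42 = 71 days; ratio 71/44 = 1.6.

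**Surgery.** Every IV non-serious window closes by Day -7 at the latest, so Day 0 is always outside it. The oral window closes on Day +6, so Day 0 and the early postoperative days are inside. For serious events after a single infusion, Day 0 is inside when infusion day + 30 is at least 0, that is, for infusions on or after Day -30. After divided infusions it is inside throughout (Day +2 to +16).

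**Do both IV patterns arise?** With the protocol's formula above 35 kg and an assumed Hb of 120 g/L:
- At an assumed 36 kg: 36 x (150 - 120) x 0.24 + 500 = 759 mg, above the single-dose limit of 20 x 36 = 720 mg, so divided.
- At an assumed 50 kg: 50 x 30 x 0.24 + 500 = 860 mg, below 1000 mg, so single.

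Both must be allowed for.

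**Phosphate.** Section 2.3.1 says that low phosphate appears more often with ferric carboxymaltose, and section 5.2 excludes patients who have it at screening. The first scheduled test after infusion is on Day 0. That is 14 to 28 days after the IV non-serious window closes (7 to 21 if divided), but inside the oral window. A non-serious low value dated by its detection on Day 0 would be recordable in the oral arm only.

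**The case against.** The best defence is that the narrow rule may never operate. The broad statement in section 8.3.4, the enquiry at each visit and the Schedule row all point to recording through follow-up in both arms. Section 8.3.6 requires any serious event to be reported at once and gives no end date. This stands, and it is why the point is a contradiction to reconcile rather than a settled unequal design. It does not remove the problem: the cut-off is the only sentence that states an end date, and staff could reasonably apply it.

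A reader might infer that IV patients are observed for about a week and oral patients for four to six weeks, so that oral iron would show four to six times as many events. The documents do not support that. The contrast applies only to non-serious events counted from first dose after a single infusion (7 v 27 to 41 days). With divided dosing it is 14 v 27 to 41 days, about 2 to 3 times. From consent it is about 2.3 times, and for serious events 1.6 times. Turning a ratio of days into a ratio of events also needs an equal daily event rate, which nothing in the protocol supports.

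Nor is surgery always outside the IV serious-event window, as shown above. A low phosphate first found at the final visit would fall outside both arms' windows, so it does not separate the arms. Phosphate values are kept on the data forms however events are coded, so only the Day 0 coding point remains.

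On ascertainment, the Appendix E grid ("How many days per week did your child experience the following symptoms") goes to oral patients only, but it belongs to a compliance form. The IV arm alone has vital signs monitored during the infusion and for 45 minutes after it. This imbalance runs both ways and is secondary.

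Finally, safety is not a listed endpoint, section 9.4.4 says the study is not powered for it, and section 8.3.5 does not say that published incidence will be by arm. All true. But the ethics-committee review is by arm, and low power does not excuse unequal observation.

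**Conclusion.** The point holds as a contradiction whose explicit half depends on arm. Under the cut-off, non-serious recording always ends before surgery for IV and on Day +6 for oral. Serious-event recording ends on Day -5 to +9 for a single infusion (Day +2 to +16 if divided) against Day +29 for oral.

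This assumes that sites apply the cut-off literally, that infusions fall on Day -35 to -21 with any second dose a week later, and that oral patients continue to Day -1. A patient who stops oral iron early would have an earlier close, so the window would then also depend on tolerance.

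It should be corrected because it can distort the safety comparison. It does not touch the haemoglobin primary endpoint.

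**What to change.** Replace the cut-off sentence in section 8.3.4 with one calendar window for both arms and for both serious and non-serious events, from informed consent to the final study visit. This keeps the present start and matches the Schedule row. From Day -42 to Day 63 it would give 63 + 42 = 105 nominal days in each arm, with surgery inside both.

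The end point needs one reconciliation first: the Schedule places the final visit at Day 63 +/- 14, while section 8.1 places it at 12 weeks +/- 4 weeks.

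Tabulate events by arm separately for the pre-surgery and post-surgery periods, so that effects near dosing are not buried under postoperative events.

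Optionally, give the Appendix E symptom grid to both arms for the same weeks.

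The main change is one sentence. The visits and the event review already exist, so the cost is slightly more event entry, plus one form if the optional step is taken.

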#### 6.1.2. DOSING AND ADMINISTRATION

##### IV Ferric Carboxymaltose

The following dosing guidelines are per the product information guide produced by the manufactures of ferric carboxymaltose.

Using the Ganzoni Formula to estimate total iron deficit:

Total iron dose (mg iron) = Weight(kg) x (Target Hb\* - Actual Hb)(g/L) x 0.24 + Iron for stores\*\*

Where:

\* Target Hb <35kg = 130g/L  
>35kg = 150g/L

\*\* Iron for stores <35kg = 15mg/kg  
>35kg = 500mg

The above calculated dose will be administered in the Medical Day Unit according to the CMI and manufactures guidelines.

A single ferric carboxymaltose administration should not exceed 1000mg or 20mg/kg as per the manufactures recommendation. It is advised that those patients requiring larger doses receive their iron replacement in two divided doses administered 1 week apart.

Oral Iron Supplements

Dosing is based on the AMH Children's Dosing Companion Guidelines:

- 1 month - 18 years, oral 3-6 mg/kg (maximum 200 mg) daily of elemental iron

In consultation with the haematology department at the Women's and Children's Hospital the following doses of oral iron are suggested:

1. To increase tolerability and patient compliance, the iron supplementation will be started at half the recommended dose (3mg/kg/day) for 5 days.
2. Once drug tolerance is established (Day 6) the patient are will be instructed to increase to a full dose (6mg/kg/day - maximum 200mg elemental iron) to be taken until the day before surgery.

The following Dose banding has been done to achieve supplementation within 90-110% of the intended dose:

- **Prescribing of oral ferrous sulfate liquid for 12 hourly dosing:**

Ferrous sulfate 6mg/mL elemental iron - 12 hourly dosing		
Patient weight (kg)	Days 1-5 (dose in mL)	Day 6 -until surgery (dose in mL)
10	2.5	5
11	3	5
12	3	6
13	3	6
14	3.5	7
15	3.5	7
16	4	8
17	4	8
18	4.5	9
19	4.5	9
20	5	10
21	5	10
22	5.5	11
23	5.5	11
24	6	12
25	6	12
26	6.5	13

Ferrous sulfate 6mg/mL elemental iron - 12 hourly dosing		
Patient weight (kg)	Days 1-5 (dose in mL)	Day 6 -until surgery (dose in mL)
27	6.5	13
28	7	14
29	7	14
30	7.5	15
31	7.5	15
32 and above	8	16

- **Prescribing of oral ferrous sulfate liquid for 8 hourly dosing:**
  - In patients who experience gastrointestinal side effects (nausea, abdominal pain) it may be beneficial to administer the dose in 3 divided doses (8 hourly).

Ferrous sulfate 6mg/mL elemental iron - 8 hourly dosing		

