## 7. STUDY INTERVENTION DISCONTINUATION AND PARTICIPANT DISCONTINUATION/WITHDRAWAL

### 7.1. DISCONTINUATION OF STUDY INTERVENTION

Discontinuation from oral or IV iron does not mean discontinuation from the study, and remaining study procedures should be completed as indicated by the study protocol. If a clinically significant finding is identified (including, but not limited to changes from baseline iron studies or haemoglobin) after enrolment, the investigator or qualified designee will determine if any change in participant management is needed. Any new clinically relevant finding will be reported as an adverse event (AE).

The data to be collected at the time of study intervention discontinuation will include the following:

- Oral iron compliance questionnaire
- Documentation of side effects or adverse reactions
- Repeat haemoglobin and iron studies to advise patient of need to continue iron therapy outside of the study

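### The non-serious adverse-event window in Section 8.3.4 closes before surgery in the IV arm but on Day 6 after a completed oral course, and it conflicts with other recording rules in the protocol

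*Protocol*

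**What the plan says.** Section 8.3.4 opens recording at consent and closes it "until 7 (for non-serious AEs) or 30 days (for SAEs) after the last day of iron therapy". The sentence selects events by start date and applies to reportable events, a term the protocol does not define.

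The same section also gives two instructions without an end date: "All AEs occurring while on study must be documented appropriately regardless of relationship" and "At each study visit, the investigator will inquire about the occurrence of AE/SAEs since the last visit". In the Schedule of Activities (Section 1.3), the row "Adverse event review and evaluation" has an entry at the final visit, Day 63 +/- 14.

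Four other sections call for recording or reporting with no time limit:
- Section 7.1 makes any new clinically relevant finding after enrolment an adverse event.
- Section 8.2 has all adverse events under IV treatment entered on the data sheet.
- Section 8.3.5 has all adverse events collated from the sheets completed at each visit, and their incidence published.
- Section 10.1.6 sends all adverse effects and complications to the medical monitor and has them presented at least twice a year by arm.

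On treatment timing, Section 8.1 states for the oral arm: "Patients will take their oral iron supplementation as prescribed starting from 3-5 weeks preoperatively until the day before surgery". IV appointments "will be made 3-5 weeks preoperatively". Under Section 6.1.2, patients who need more than the single-dose maximum "receive their iron replacement in two divided doses administered 1 week apart". Section 7.1 adds: "Discontinuation from oral or IV iron does not mean discontinuation from the study".

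**The concern.** A window tied to the last iron day gives each arm its own calendar period. Both arms have the same operation on Day 0, and the operation itself produces minor events. If one arm's window includes surgery and the other's does not, a comparison of non-serious event rates mixes the effect of the iron with the effect of the operation.

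This matters because the protocol weighs the added risk and cost of IV iron against its benefit (Sections 2.2, 2.3.3 and 4.2), and the published event rates are the trial's own evidence on that risk. The rule decides what is recorded, not only what is analysed. A later analysis plan cannot recover events that were never written down.

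The conflict inside Section 8.3.4 is a second problem. Two members of staff could follow the same section correctly and record different events.

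**Working it through.** The protocol gives no closing day per arm, so there is no figure to reproduce. The closing days follow from its timings, with surgery as Day 0.

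**Inputs**
- Window length after the last iron day: 7 days (non-serious), 30 days (serious). Section 8.3.4.
- IV single dose: Day -28 +/- 7, so Day -35 to Day -21. Sections 1.3 and 8.1.
- IV split dose: second dose 7 days after the first, so Day -28 to Day -14. Section 6.1.2.
- Completed oral course: last dose on Day -1. Sections 6.1.2 and 8.1.

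**Closing day = last iron day + window length**

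| Regimen | Last iron day | Non-serious closes | Serious closes |
|---|---|---|---|
| IV, single dose | -35 to -21 | -28 to -14 | -5 to 9 |
| IV, split dose | -28 to -14 | -21 to -7 | 2 to 16 |
| Oral, completed | -1 | 6 | 29 |

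**Difference between arms.** For non-serious events the smallest difference is 6 - (-7) = 13 days and the largest is 6 - (-28) = 34 days.

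**When surgery is covered.** Day 0 is inside the non-serious window only if last iron day + 7 >= 0, that is, if the last iron day is Day -7 or later. The latest permitted IV infusion, Day -14, misses this by 7 days. A completed oral course meets it, and its window covers Day 0 to Day 6. An oral patient who stops before Day -7 does not meet it.

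**Sensitivity to the split-dose reading.** If both doses had to fall inside the Visit 2 window, the last IV day would be Day -21 at the latest and the window would close by Day -14. The smallest difference would then be 6 - (-14) = 20 days.

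**Conflict with the visit schedule.** Visit 3 is at Day 21 - 7 = Day 14 at the earliest, after every non-serious window has closed. The final visit is at Day 63 - 14 = Day 49 at the earliest. By then the window has been closed for 49 - 6 = 43 days in oral completers and for 49 - (-7) = 56 to 49 - (-28) = 77 days in the IV arm. No non-serious event starting between these two visits falls inside the window in either arm, yet the section has staff ask about new events at each visit.

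**The case against.** The best reply is that the window sentence stands alone. The rest of Section 8.3.4, together with Sections 1.3, 7.1, 8.2, 8.3.5 and 10.1.6, points to recording throughout the study. Staff may follow those, and the undefined term reportable events may mean a narrower class, in which case the sentences need not conflict. This has force. A reader might infer that postoperative events will be recorded in the oral arm only; the documents support this only as a risk under one of two competing rules. But no text ranks the rules or defines the term, so the ambiguity stands.

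It can also be said that a fixed period after last exposure is a usual rule and gives both arms equal post-treatment follow-up. That is true, but here it places an operation common to both arms inside one arm's window only. Late enquiry does keep a purpose, since events are followed until they resolve; that does not explain asking about new ones. The trial is not powered for safety (Section 9.4.4), and Section 8.3.5 promises incidence rather than a formal test. Both points limit the consequence without removing the unequal observation.

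Three further readings go too far:
- *A low phosphate first found on Day 0 would count in the oral arm only.* The window works on start dates, and Section 1.3 schedules no electrolytes between Visit 1 and Day 0. The start is therefore unknown and, in an IV patient, may lie inside the window. Laboratory values are entered in any case (Section 10.1.8.1).
- *Serious events would be lost.* The serious-event windows differ too, but Section 8.3.6 sends every serious event to the ethics committee.
- *The bias has a known direction.* Section 8.3.3.2 allows an event to be classed as unrelated when another cause is established, and oral patients who stop early lose the extra coverage.

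**Conclusion.** The point holds as a defect in how non-serious adverse events are ascertained. Applied as written, the window closes before surgery under every permitted IV schedule and on Day 6 after a completed oral course, so only oral completers are observed over Day 0 to Day 6. The sentence also conflicts with the rest of its own section and with the final-visit review, and nothing settles which governs. The published incidence therefore depends on the rule that staff follow.

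The closing days assume that IV timing stays within Day -35 to Day -21 for the first dose, that a second dose follows one week later where needed, and that the oral course is completed. The documents give no basis for estimating how many events would be missed. The primary and secondary efficacy endpoints are not affected. This should be corrected, but it does not threaten the trial's main conclusion.

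**What to change.** In Section 8.3.4, replace the window sentence with one calendar period for both arms: every adverse event, serious or not, that starts between consent and the final study visit is recorded. Report events with onset before surgery and from surgery onwards separately by arm. This removes the conflict with the rest of the section and with the Schedule of Activities. Tie the end to the final visit itself rather than to a day number, because Section 1.3 places that visit at Day 63 +/- 14 and Section 8.1 at 12 weeks +/- 4 weeks.

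The change needs no new visit or blood sample, since enquiry at each visit is already planned. It does cost something: more minor postoperative events to record in both arms, and probably an adverse-event entry on the Appendix D visit sheets, which show no such field.

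The change does not equalise everything. The Appendix E symptom questionnaire goes to the oral arm only, so events known only from it should be tabulated separately and kept out of the comparison between arms.
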